8.5 Multiple Comparisons/Multiplicity

To control familywise type-I error, the hypothesis tests for treatment difference between DCC-2618 and placebo will be performed at two-sided 0.05 level of significance sequentially in the following order:

1. The primary endpoint PFS based on independent radiologic review
2. The key secondary endpoint ORR based on independent radiologic review
3. OS
4. QOL as determined by changes from baseline to Day 1 of Cycle 2 in EORTC-QLQ-C30 Role function and Physical function (each at 0.025 level of significance)

If any hypothesis test is not significant at $\alpha=0.05$ level, the subsequently listed analyses will be viewed as descriptive.

8.6 Examination of Subgroups

Subgroup analysis will be performed for the primary and key secondary efficacy endpoints defined by the following variables:

- Age (18 – 64 vs 65 – 74 vs 75 years or older)
- Gender (Male vs female)
- Race (White vs non-White vs not-reported)
- Region (US vs non-US)
- Screening ECOG (0 vs 1/2)
- Number of prior therapies (3 vs ≥ 4)

8.7 Interim Analysis and Data Monitoring

No interim analysis for efficacy will be performed for this study. An IDMC will be used to review safety data periodically throughout the course of this study.

The IDMC will consist of an experienced biostatistician and two qualified clinicians, who are not employees of the Sponsor, with combined scientific expertise in general oncology and GIST and practical experience conducting clinical studies and monitoring safety and efficacy of clinical studies. The IDMC or Sponsor may request an ad hoc meeting for any reason, including significant unexpected safety event, unplanned unblinding of study results, follow-up of an observation during a planned IDMC meeting, or a report external to the study, such as publication of study results from a competing product. The IDMC objectives and operational details will be defined in the IDMC Charter.

9 PHARMACOKINETICS

Individual patient's raw concentrations of DCC-2618 and actual sampling time will be listed by nominal sampling time point. Raw concentrations for each nominal sampling time point will be summarized with descriptive statistics such as number of subjects, geometric mean, median, arithmetic mean, standard deviation, coefficient of variation, and geometric coefficient of variation, minimum and maximum.

10 SAFETY ANALYSIS

10.1 Study Drug Exposure

The duration of initial assigned study treatment in weeks, total dose, average daily dose, and relative dose intensity will be displayed using continuous descriptive statistics. In addition, the number and percent of patients in categories based on treatment duration and patients with dose increase, reduction, and interruption will be summarized.

The treatment duration will be calculated as (the date of last treatment before Open label or discontinuation treatment – date of first treatment of study drug + 1 day)/7. If the date of last treatment is missing because the true last treatment date is unknown or patients are still on treatment at the time of analysis, the earliest of the end of treatment (EOT) date, end of study date, death date, and data cut-off date will be used. The average daily dose will be calculated as the total dose received divided by treatment duration in days. The relative dose intensity (%) is the total dose received divided by the total planned dose and multiplied by 100%. These analyses will be performed for the Safety population.

10.2 Adverse Events

Adverse events tables will summarize the number and proportion of patients overall and by treatment arm with an event by each system organ class (SOC) and preferred term (PT) for the Safety population. All tables will only include treatment emergent adverse events (TEAEs), where TEAEs are defined as any AE that occurs that occurs after administration of the first dose of study drug and through 30 days after the last dose of study drug. In the case of missing start and/or stop date, non-missing date parts will be used to determine if an AE is treatment-emergent or not. An AE will be categorized as TEAE if a determination cannot be made using the non-missing date parts as to when the event occurred relative to study drug administration. Adverse event toxicity grade will be classified using the National Cancer Institute Common Terminology Criteria for Adverse Events (NCI-CTCAE) Version 4.03 criteria. For incidence summaries, a missing toxicity grade of a TEAE will be conservatively imputed as severe; for a TEAE missing causal relationship to study treatment, a causality of “related” will be assigned. Listings will include all reported AEs, flagging events that were TEAEs and displaying missing severity grades and causalities as they were entered in the clinical database.

An overall summary of the number of subjects with TEAEs as well as the number of event will be presented, including the number and percentage of subjects with any TEAEs, treatment-emergent serious adverse events (SAE), drug-related TEAEs and TEAEs leading to treatment discontinuation, study discontinuation, and death.

The number and percentage of patients reporting TEAEs, as well as the number of events, in each treatment group will be tabulated by SOC and PT; by SOC, PT, and maximum severity. If a patient has multiple occurrences of the same SOC and PT, then the patient will be counted only once for the SOC and PT using the most severe occurrence for the summarization by maximum severity. Presentation by SOC and PT will display SOC sorted alphabetically and PT by descending frequency within SOC.

TEAEs and drug-related TEAEs will be summarized by PT by descending frequency. Treatment-emergent SAEs, TEAEs leading to study treatment discontinuation and study discontinuation, and treatment-emergent SAEs leading to death will be summarized by SOC, PT, and treatment arm.

Adverse events of special interest (AESI) are serious or nonserious AEs of scientific and medical concern specific to study drug, for which ongoing monitoring and immediate notification by the Investigator to the Sponsor is required. AESIs will be flagged on the eCRF by the investigator. The following AEs are considered AESIs: squamous cell carcinoma of skin (SCC), actinic keratosis, and keratoacanthoma.

The number and percentage of patients by treatment arm with the following categories of TEAEs will be summarized in tables by SOC and PT:

- Any TEAE
- Any TEAE by toxicity grade
- Any TEAE Grade 3/4
- Any drug-related TEAE
- Any treatment-emergent SAE
- Any drug-related treatment-emergent SAE
- Any TEAE leading to dose modification(dose reduction or interruption)
- Any TEAE leading to treatment discontinuation
- Any TEAE leading to study discontinuation
- Any TEAE leading to death
- Any AESI
- Any AESI by toxicity grade
- Any AESI Grade ≥ 3
- Any drug-related AESI

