9. STATISTICAL CONSIDERATIONS

9.1. Determination of Sample Size

The sample size selection of approximately 120 patients (n=80 DCC-2618, n=40 placebo) was based on considerations for powering of the primary endpoint, key secondary endpoint, detection of rare safety events and overall exposure to DCC-2618, and assuming 15% patient dropout. Patients will be randomized in a 2:1 ratio of DCC-2618 versus placebo.

This sample size [105 patients (n=70 DCC-2618, n=35 placebo) with 90 events (55 DCC-2618, 35 placebo) at the final analysis] will have at least 90% power to detect a difference in PFS between DCC-2618 and placebo assuming a median PFS of 4.5 months for DCC-2618 and 1 month for placebo. Moreover, this assumes 9 months of uniform recruitment and 6 additional months of follow-up (total patient follow-up of 15 months).

Furthermore, 105 patients (n=70 DCC-2618, n=35 placebo) will have approximately 80% power to detect a 0.2 difference in ORR assuming that the ORR for DCC-2618 = 0.22 and the ORR for placebo = 0.02.

In addition, a minimum sample size of 80 DCC-2618 patients allows adequate power to detect the incidence of rare safety events. A sample of 80 patients yields 95% probability that the study will reveal at least one occurrence of all safety events that occur in patients at a rate of 4.0% or greater. This in combination with the exposure to DCC-2618 from other studies conducted in this clinical program will meet the recommendations for overall exposure recommended by FDA.

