2.3 Determination of Sample Size

The sample size selection of approximate 120 patients (n=80 DCC-2618, n=40 placebo) was based on considerations for powering of the primary endpoint, key secondary endpoint, detection of rare safety events and overall exposure to DCC-2618, and assuming 15% patient dropout. Patients will be randomized in a 2:1 ratio of DCC-2618 versus placebo.

This sample size [105 patients (n=70 DCC-2618, n=35 placebo) with 90 events (55 DCC-2618, 35 placebo) at the final analysis] will have at least 90% power to detect a difference in PFS between DCC-2618 and placebo assuming a median PFS of 4.5 months for DCC-2618 and 1 month for placebo. Moreover, this assumes 9 months of uniform recruitment and 6 additional months of follow-up (total patient follow-up of 15 months).

Furthermore, 105 patients (n=70 DCC-2618, n=35 placebo) will have approximately 80% power to detect a 0.2 difference in ORR assuming that the ORR for DCC-2618 = 0.22 and the ORR for placebo = 0.02.

In addition, a minimum sample size of 80 DCC-2618 patients allows adequate power to detect the incidence of rare safety events. A sample of 80 patients yields 95% probability that the study will reveal at least one occurrence of all safety events that occur in patients at a rate of 4.0% or greater. This in combination with the exposure to DCC-2618 from other studies conducted in this clinical program will meet the recommendations for overall exposure recommended by FDA.

Where required, safety personnel at the Sponsor or designee may be unblinded to a patient's study drug assignment to meet reporting requirements to regulatory agencies. In addition, the Investigator, patient, Sponsor, and study team will be unblinded at the time the patient has disease progression by modified RECIST based on independent radiology review.

At no point in time before official full study unblinding will any efficacy and safety analyses be conducted by the Sponsor or Sponsor representatives, unless there is explicit permission to do so, for instance high level efficacy assessment for the purposes of an Independent Data Monitoring Committee (IDMC) review to determine the adequacy of the risk/benefit profile of the drug as it pertains to the conduct of the clinical trial.

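### Adverse event results are compared between arms without a person-time denominator, although the design implies roughly 2- to 3.5-fold more observation time on DCC-2618

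*SAP*

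**What the plan says.** SAP 10.2 sets the AE summary measure: "Adverse events tables will summarize the number and proportion of patients overall and by treatment arm with an event". For TEAEs it also tabulates the number of events by system organ class and preferred term, and in an overall summary. The closing list of categories, which includes SAEs and AESIs, is given as number and percentage of patients by arm. TEAEs run from first dose to 30 days after the last dose.

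SAP 10.1 describes exposure separately, starting with "The duration of initial assigned study treatment in weeks". That duration stops at the last dose before open-label treatment or discontinuation. It is not linked to the AE tables.

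SAP 2.2.2 keeps patients on blinded treatment until progression by independent review, unacceptable toxicity or withdrawal. SAP 3.1 ends the double-blind period of a crossover patient on the day before the first DCC-2618 dose. It also says that safety against placebo will be judged mainly on double-blind data. Protocol 9.1 powers the trial "assuming a median PFS of 4.5 months for DCC-2618 and 1 month for placebo". Protocol 9.8.6.1 plans no formal test of AE incidence.

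Neither document plans an exposure-adjusted rate, a time-to-first-event analysis of AEs, or AE incidence over a common early window.

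**The concern.** The proportion of patients with an event grows with the time they are watched. Here the watching time depends on efficacy: the better the drug delays progression, the longer its arm stays in the double-blind AE tables. Part of any excess on DCC-2618 would then reflect longer observation, and the planned tables do not show how much. Since SAP 3.1 makes these tables the main safety comparison with placebo, the benefit-risk reading depends on them even though nothing is tested.

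**Working it through.** **Inputs from the documents.** Median PFS 4.5 and 1 month; 9 months of uniform recruitment plus 6 months of follow-up; 70 and 35 evaluable patients (Protocol 9.1, SAP 2.3). Scans every 28-day cycle through Cycle 4, then every other cycle (Protocol Table 1, note 21). TEAE window of 30 days after last dose (SAP 10.2).

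**Assumptions not in the documents.** Exponential PFS; treatment stops only at progression or cut-off; no exposure lost to dropout; equal and constant AE hazard in both arms.

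**1. Reproduce the plan's event split.** Hazards are λ = ln 2/4.5 = 0.154 and ln 2/1 = 0.693 per month. Administrative censoring is uniform on 6 to 15 months, so

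P(event) = 1 − [exp(−6λ) − exp(−15λ)]/(9λ) = 0.785 and 0.9975.

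Expected events are 70 × 0.785 = 55.0 and 35 × 0.9975 = 34.9, which agrees with "with 90 events (55 DCC-2618, 35 placebo) at the final analysis". The exponential model is therefore consistent with the plan.

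**2. Mean observation time.** Mean treatment time to the cut-off is P(event)/λ: 0.785/0.154 = 5.10 months and 0.9975/0.693 = 1.44 months. The other rows come from simulation (2,000,000 patients per arm).

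| Observation time | DCC-2618 (months) | Placebo (months) | Ratio |
|---|---|---|---|
| On treatment, planned cut-off | 5.10 | 1.44 | 3.5 |
| Same, progression found at scans | 5.67 | 2.03 | 2.8 |
| On treatment plus 30-day window, both arms | 5.86 | 2.42 | 2.4 |
| Scans plus 30-day window, both arms | 6.39 | 3.01 | 2.1 |

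SAP 3.1 can cut the 30-day window short when a patient moves to open-label treatment. If the window counted on DCC-2618 only, the ratio would be 4.1 (3.1 with scans). If it counted on placebo only, it would be 5.10/2.42 = 2.1 (5.67/3.01 = 1.9 with scans). These are extremes.

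**3. Crude proportions under equal hazards.** With AE hazard r, the expected proportion is the mean of 1 − exp(−r × time). Each cell shows DCC-2618 versus placebo, and the ratio.

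| Observation time | r = 0.05 per month | r = 1 per month |
|---|---|---|
| On treatment | 21.2% vs 6.7% (3.2) | 86.6% vs 59.1% (1.5) |
| With scans | 23.5% vs 9.4% (2.5) | 92.1% vs 76.3% (1.2) |
| With window | 24.3% vs 11.2% (2.2) | 95.0% vs 84.7% (1.1) |
| With scans and window | 26.3% vs 13.7% (1.9) | 97.0% vs 91.2% (1.1) |

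The true rate ratio is 1 in every cell.

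**4. Can the rate be recovered from the planned outputs?** Suppose AE rates are equal and the window applies in both arms. Event counts per patient then have ratio 2.42, while SAP 10.1 duration has ratio 3.54. Dividing gives 2.42/3.54 = 0.68, a false deficit on DCC-2618. With the window on DCC-2618 only, it gives 4.07/3.54 = 1.15. Numerator and denominator cover different periods, and the counts include repeat events within a patient.

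**The case against.** **The comparison is descriptive, and the bias is conservative.** No AE test is planned, no decision rule is affected, and the artefact overstates toxicity rather than hiding it. This stands, and it limits the severity. It does not make the tables easier to read.

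**Counts and duration are both reported.** It would therefore be too strong to say that every comparison is a crude proportion, or that a reader has nothing with which to judge exposure. Step 4 shows, however, that the derived rate can be wrong in either direction.

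**The remedy has its own bias.** Suppose an event occurs only in the first two weeks, with true risk 20% on DCC-2618 and 10% on placebo (assumed figures, mean onset 0.23 months). With the 30-day window, first-event rates are 0.20/(0.8 × 5.86 + 0.2 × 0.23) = 4.2 and 0.10/(0.9 × 2.42 + 0.1 × 0.23) = 4.5 per 100 patient-months. A true doubling of risk disappears, while the crude proportions show it. This is a real limit. It argues for showing both measures, not for omitting the rate.

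**Skin AESIs.** A reader might infer that skin-cancer AESIs accumulate with time and are the worst case. The documents do not say so, and if they do accumulate, a constant-hazard rate fits them poorly. What the documents do show is that scheduled on-treatment skin examinations start at Cycle 3 Day 1 (Protocol Table 1, note 14), with another at end of treatment. Under the planning medians about 75% of DCC-2618 and 28% of placebo patients would be progression-free at day 56. Detection opportunity therefore also differs by arm, and a rate does not fully remove that.

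**Conclusion.** The point holds as a cheap improvement. The plan compares AEs between arms without a person-time denominator, in a design whose own assumptions imply roughly 2- to 3.5-fold more mean observation time on DCC-2618. At 0.05 events per month, equal hazards would appear as a 1.9- to 3.2-fold excess. At 1 per month the artefact is only about 1.1- to 1.5-fold, so a large excess is not a general result.

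A reader might infer that blinded exposure differs 4.5-fold. The documents give no exposure ratio: 4.5 is the ratio of assumed median PFS. Using it as an exposure ratio ignores the data cut-off, scan timing and the 30-day window. The same shortcut would give 0.05/(0.05 + 0.154) = 24.5% versus 0.05/(0.05 + 0.693) = 6.7%, about 3.7-fold, which is above all four rows in step 3.

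The figures rest on exponential PFS, constant equal AE hazards and treatment ending only at progression or cut-off. Dropout, or reaching 90 events sooner with all 120 randomized patients, would lower the ratios.

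**What to change.** Keep the crude tables. Add to SAP 10.2, for the double-blind period and by arm, exposure-adjusted incidence rates with 95% confidence intervals for TEAEs, Grade 3 or higher TEAEs, SAEs and AESIs. Define the rate as patients with a first event per 100 patient-months at risk.

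Run time at risk from first dose to the earliest of:
- first event of that type;
- 30 days after last dose (end of the TEAE window);
- the day before the first open-label DCC-2618 dose, or other end of the double-blind period under SAP 3.1;
- death;
- data cut-off.

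Count only events inside that time, so that numerator and denominator match. State in the SAP that the rates assume a roughly constant hazard, can dilute early-onset toxicity on the longer-exposed arm, and supplement the crude proportions without replacing them.

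The cost is a few extra tables from dates already collected. Design, conduct and clinical rules do not change.

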10.3 Eastern Cooperative Oncology Group Performance Status

The Eastern Cooperative Oncology Group (ECOG) Performance Status Assessments will be summarized for each visit.

10.4 Clinical Laboratory Data

Clinical laboratory measurements will be collected from screening until the EOT visit (within 7 days of the last dose). Laboratory values will be graded for toxicity as defined by the NCI-CTCAE, Version 4.03 or higher.

Table 2. Safety Laboratory Tests

Serum Chemistry	Hematology	Urinalysis
Glucose	Hemoglobin	Urine protein
Blood urea nitrogen	
 • Mean corpuscular hemoglobin 	Urine blood
Creatinine	
 • Mean corpuscular hemoglobin concentration 	Specific gravity
Sodium	
 • Mean corpuscular volume 	Urine ketones
Potassium	Hematocrit	Urine glucose
Calcium	Platelets	
Magnesium	Leukocytes	
Phosphorus	Reticulocytes	
Total and direct bilirubin	Differential (absolute):	
Alkaline phosphatase	
 • Eosinophils 	
Aspartate aminotransferase	
 • Basophils 	
Alanine aminotransferase	
 • Neutrophils 	
Lactate dehydrogenase	
 • Lymphocytes 	
Total protein	
 • Monocytes 	
Albumin	Coagulation Studies (for patients taking anticoagulants)	
Creatine Phosphokinase	
 • Activated partial thromboplastin time 	
Globulin	
 • Prothrombin time 	
Triglycerides	
 • International Normalized Ratio 	
Lipase		
Amylase		
TSH		
T3		
T4		

Assessments will be summarized overall by time point utilizing continuous descriptive statistics. In addition, the change as well as shift in toxicity grade from baseline will be summarized for continuous parameters. For categorical parameters, the n and percentage will be displayed.

Numeric laboratory values recorded as “<x” or “>x” will be handled as follows,

- In the listings, “<x” and “>x” will be presented as recorded
- In the summary tables of observed values and changes from the baseline and those for shifts in CTCAE grade, “<x” and “>x” will be converted to numeric values before the analysis,
 - “<x” will be converted to “x – 1e-6”
 - “>x” will be converted to “x + 1e-6”

In the summary tables of numeric values, the convention is to present 1 decimal place beyond those used in raw data for median and mean and 2 more decimal places beyond those used in

raw data for standard deviation and standard error. There will be no deviation from this convention to display 6 or more decimals due to any conversion using the above rules.

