9.8.6. Safety Analysis

9.8.6.1. Adverse Events

Adverse events will be summarized utilizing the number and proportion of patients overall and by period (randomized/open-label), system organ class and preferred term for the Safety population. All tables will only include TEAEs, where treatment emergent is defined as any AE that occurs after administration of the first dose of study drug and through 30 days after the last dose of study drug, but listings will include all AEs.

Adverse event toxicity grade will be classified using NCI-CTCAE Version 4.03 criteria (See [Table 13](#)). If a patient has multiple occurrences of the same system organ class (SOC) or preferred term, then only the most severe event will be summarized in the tables for that SOC and preferred term. Adverse events of \geq Grade 3 will also be summarized. A missing toxicity grade will not be imputed.

The AE analysis will be repeated for SAEs, AEs leading to dose reduction or discontinuation, and AESIs.

No formal hypothesis-testing analysis of AE incidence rates will be performed.

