As of the primary efficacy analysis, the evaluation of the efficacy and safety of DCC-2618 against the placebo will be mainly based on the data collected during the double-blind treatment analysis period. The analysis during this period will be detailed in [Sections 3.2 to 10.10](#).

For data collected during the open-label analysis period and entered in the database by the data cut-off date or at the final database lock, statistical analysis will be described in [Section 11](#).

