10.6 Electrocardiograms

PR, QRS, QT, QTc (ie, QTcB and QTcF) and RR intervals and their change from baseline will be summarized for each treatment group by scheduled visit. Patients will be categorized into > 450 , > 480 , and > 500 ms per their maximum post-baseline absolute QTc interval and > 30 and > 60 ms per their maximum change from baseline QTc interval. Additionally, patients will be classified into the following categories: HR ≤ 50 bpm and/or decrease from baseline ≥ 20 bpm; HR ≥ 120 bpm and/or increase from baseline ≥ 20 bpm; PR ≥ 220 ms and/or increase from baseline ≥ 20 ms. The number and percentage of subjects in each category will be summarized for each treatment group.

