10.7 Echocardiograms/Multigated Acquisition Scans

Summary and change from baseline for left ventricular ejection fraction (LVEF) will be summarized overall by time point utilizing descriptive statistics. Change from baseline in LVEF will be summarized with number and percentage of patients who have a $>20\%$ absolute decrease from baseline as well.

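### Three safety-table rules in SAP section 10 (Grade 3/4 with imputed grades, the coagulation label, tables with no arm named) conflict with the protocol or with the SAP's aim of judging safety against placebo

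*SAP*

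**What the plan says.** **Severe adverse events.** The list of by-arm TEAE tables in SAP 10.2 includes "Any TEAE Grade 3/4". The same section states that for incidence summaries "a missing toxicity grade of a TEAE will be conservatively imputed as severe". Protocol 9.8.6.1 asks for a summary of events of Grade 3 and above, and says "A missing toxicity grade will not be imputed". For adverse events of special interest, the SAP's own list uses Grade 3 or higher.

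**Coagulation.** SAP Table 2, in section 10.4, heads the coagulation tests "Coagulation Studies (for patients taking anticoagulants". The coagulation row of Protocol Table 1 marks screening, Cycle 1 Day 1, Day 1 of later cycles and end of treatment for all patients. Footnote 7 gives anticoagulated patients a further test at Cycle 1 Day 15.

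**Level of summary.** For laboratory data, SAP 10.4 says "Assessments will be summarized overall by time point utilizing continuous descriptive statistics". SAP 10.5 uses the same formula for vital signs, and SAP 10.7 says that LVEF "will be summarized overall by time point utilizing descriptive statistics". None of these names a treatment arm, and neither do 10.3 (ECOG) and 10.8 (dermatology). By contrast, the ECG intervals in 10.6 "will be summarized for each treatment group by scheduled visit", and 10.2 names overall and by-arm summaries as two separate levels. SAP 3.1 says that "the evaluation of the efficacy and safety of DCC-2618 against the placebo" will rest mainly on the double-blind period.

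**The concern.** A programmer builds tables from the sentences in section 10. Followed to the letter, they give three results that the protocol or the SAP's own aim does not support.

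- The main severe-TEAE table would count a different set of patients from the one the protocol defines: fatal events out, ungraded events in.
- Coagulation results from patients not on anticoagulants would be collected at every scheduled visit but not summarised. The subgroup left is the hardest to interpret. Under inclusion criterion 10 its PT/INR may already exceed the entry limit, and Protocol 5.12.3.2 warns that study drug may affect warfarin through CYP2C9.
- Laboratory, vital-sign and LVEF changes, which Protocol 9.2.2.2.2 names as safety endpoints, could appear in one pooled column. Placebo patients are expected to leave initial treatment much sooner, so the mix of arms in that column would change from visit to visit.

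**Working it through.** **The plan's own safety figure.** SAP 2.3 states a 95% probability of at least one occurrence among 80 patients of an event with a 4.0% rate. 1 − 0.96^80 = 0.962, which agrees. Nothing below changes this figure.

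**(a) Severe-TEAE table, side by side.**

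| | Grades in the table | Missing grade |
|---|---|---|
| Protocol 9.8.6.1 | 3, 4, 5 | not imputed |
| SAP 10.2, all TEAEs | 3, 4 | counted as severe |
| SAP 10.2, special interest | 3, 4, 5 | counted as severe |

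Protocol Table 13 equates severe with Grade 3, so an imputed event enters the Grade 3/4 table. With the planned 80 and 40 patients, each patient left out or added moves the rate by 1/80 = 1.25 points on DCC-2618 or 1/40 = 2.5 points on placebo. The documents give no expected number of fatal or ungraded events, so the net direction is unknown. SAP section 1 says that the SAP outlines differences from the protocol's methods, but neither change is identified as one.

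**(b) Coagulation.** Protocol Table 1 schedules four kinds of visit for everyone and one additional visit for anticoagulated patients. The SAP label carries the condition for that one visit over to the whole panel. Taken literally, it removes every result from patients not on anticoagulants. The documents do not say what share of patients that is; I assume it is the majority.

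**(c) Pooling, as an illustration.** Inputs:

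- 80 and 40 patients, and median PFS of 4.5 months and 1 month (SAP 2.3)
- 28-day cycles (Protocol 5.2)
- assumptions: exponential PFS stands for time on initial treatment, there is no other dropout, and a month is 30.4375 days

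The number still on initial treatment after t months is n × 2^(−t/median).

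| Visit (Day 1) | t (months) | DCC-2618 | Placebo | Placebo share |
|---|---|---|---|---|
| Cycle 1 | 0 | 80.0 | 40.0 | 33% |
| Cycle 2 | 0.92 | 69.4 | 21.1 | 23% |
| Cycle 3 | 1.84 | 60.3 | 11.2 | 16% |
| Cycle 4 | 2.76 | 52.3 | 5.9 | 10% |
| Cycle 6 | 4.60 | 39.4 | 1.6 | 4% |

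A mean change of size d that occurs only on DCC-2618 would show in a pooled column as d × (1 − placebo share): about 0.77d, 0.84d, 0.90d and 0.96d at Cycles 2, 3, 4 and 6. A constant effect would thus appear to grow over time.

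**The case against.** The strongest reply is that pooling is not intended.

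- SAP 4.2 runs all safety analyses by treatment actually received, which has little purpose if the arms are merged.
- SAP 3.1 sets the comparison with placebo as the aim.
- SAP 11.5 analyses TEAEs and the other safety endpoints by initial treatment group even in the open-label period.
- The SAP uses the word overall loosely: in 8.3.5, EQ-5D-5L is summarised overall and then tested between arms.
- The formula is inherited from Protocol 9.8.6.3, 9.8.6.4 and 9.8.6.6.
- Clinically significant laboratory and vital-sign findings must also be recorded as adverse events (Protocol 7.7.1), and those are tabulated by arm.

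Most of this stands, and it makes (c) an ambiguity rather than a decision to pool. It does not close the gap. SAP 4.2 says which arm a patient counts in, not that tables are split by arm. SAP 3.1 passes the detail to the very sections in question. SAP 11.5 writes the by-arm display down for the open-label period, while 10.4, 10.5 and 10.7 do not do so for the randomised one.

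On (b), the phrase is a label in a list of tests, and the analysis sentence in 10.4 carries no such restriction. It probably descends from footnote 1 of Protocol Table 12. A subset could also still be compared by arm. These points stand, but the label remains narrower than the protocol's schedule.

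On (a), fatal events are not lost from the report: the same SAP list gives, by arm, TEAEs by grade and TEAEs leading to death. A patient with both a Grade 3 and a Grade 5 event might still be counted, because 10.2 states its worst-occurrence rule only for the maximum-severity summary. The imputation is stated openly, and listings show grades as entered. The mismatch with the protocol remains.

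A reader might also infer from the 2:1 allocation that a pooled table would show a DCC-2618-only LVEF decline at two thirds of its true rate. By visit, that is the wrong denominator. The first scheduled on-treatment scan is at Cycle 3 Day 1 (Protocol Table 1, footnote 13), where the illustration gives about 84%.

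**Conclusion.** The point holds at minor severity. Items (a) and (b) are textual conflicts between the SAP and the protocol, and they rest on no modelling. Item (c) is an omission that the rest of the SAP very likely resolves in favour of display by arm. Its percentages apply only to a literal pooled table, and only under the assumptions listed with them.

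A reader might go further and infer that these tables could not show the drug's effect against placebo. The documents do not support that. The adverse-event and ECG tables are expressly by arm, Grade 5 events appear by arm elsewhere in the same list, the coagulation phrase is a label, and SAP 3.1, 4.2 and 11.5 all point to by-arm presentation. No primary or key secondary result is affected.

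**What to change.** 1. In SAP 10.2, change Grade 3/4 to Grade 3 or higher. Either show missing grades as missing, as in Protocol 9.8.6.1, or keep the imputation and declare it as a departure from the protocol.
2. In SAP Table 2, delete the anticoagulant qualifier and summarise coagulation for all patients.
3. In SAP 10.4, 10.5 and 10.7, write by treatment arm and overall. Name the arm in 10.3 and 10.8 as well.

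The cost is SAP wording and table shells. No data collection, sample size or efficacy analysis changes.
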